The RCTM includes six consultation sessions over a 4-month period conducted by a trained Transition Counselor (TC) with a primary family caregiver (self-identified as the person most responsible for providing on-going assistance to the care recipient in RLTC).² Other family members may also be included in the counseling sessions based on the needs expressed by and at the discretion of the primary caregiver. Typically, these additional participants would be identified before the enrollment of the primary caregiver and thus, participate in the initial screening and consent process, often completing the study surveys as well. The first 3 sessions are held weekly and the final 3 sessions are held monthly [subject to scheduling/availability]. RCTM sessions take place either via telephone or video-based conference. The sessions focus on the experiences of the caregiver, the care recipient, and (potentially) other family members following RLTC admission. Among the objectives for each session are the caregiver's acquisition of information and strategies designed to deal with unique issues, including distance caregiving. The sessions are designed to establish a therapeutic rapport with the caregiver and the family; provide a safe environment to explore stressors; examine family relational dynamics as they relate to the RLTC placement decision itself as well as the roles different family members play in the life of the caregiver and relative in RLTC; identify new modes of communication to facilitate more effective

SOCIAL PROTOCOL (HRP-580)

PROTOCOL TITLE: The Residential Care Transition Module

VERSION DATE: 2/10/2022

interactions with other family members and care staff; and identify effective ways to advocate for improved quality of care for and quality of life of their relatives in RLTC.

Throughout the RCTM counseling process/relationship, caregivers receive constructive feedback to help achieve their goals stated at the outset of the RCTM intervention. The duration of each session is about 45 to 150 minutes each.

The following summarizes the clinical content of the semi-structured RCTM, delivered across six sessions, each of which is prioritized and tailored according to the needs expressed by the caregiver. Each component is designed to positively influence key outcome domains of RLTC admission for family caregivers: primary subjective stress; secondary role strain; care-related distress; and depressive symptoms (see below):

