Several steps will enhance study retention. Baseline and follow-up surveys are administered in a format that is convenient to ADRD caregivers (online, telephone, or mail survey/questionnaire formats). Baseline interviews are anticipated to take no more than 60 minutes; follow-up interviews are expected to take approximately 45 minutes. Quarterly follow-up calls by the TC to all participants will ask "how things are going" and will offer the opportunity for controls to feel connected to the overall study. Following completion of the final 12-month assessment, participants receive a call from one of the TCs. A handwritten note from the study team to thank each participant for their study participation will be sent out to enrolled participants after their last survey or semi-structured interview. These thank you letters will not be sent if a participant withdraws from the study. If a participant did not return all surveys as scheduled, a thank you card will be sent near the projected date of their last study survey. If a participant is enrolled in the study supplement, a thank you letter will be sent after their last survey or interview is completed. Bi-annual project newsletter will be sent to all participants. We will also pay participants \$25 following the completion of each baseline, 4-, 8-, and 12-month and final qualitative interview (if selected). Payments will be made using a pre-paid debit card, using the Greenphire ClinCard system.

SOCIAL PROTOCOL (HRP-580)

PROTOCOL TITLE: The Residential Care Transition Module

VERSION DATE: 2/10/2022

-Study schedule: Months 3-56 (see Timeline below for general guide)

-Time for participants: 45 minutes

Treatment fidelity. To guarantee accuracy of treatment delivery, [name] and [name] developed a detailed RCTM treatment manual based on the extensive preliminary work detailed above. The treatment manual will ensure consistent implementation of the RCTM in the proposed project. The manual is an ongoing reference that provides a step-by-step timeframe of delivery activities. The manual will eventually serve as a training tool for future TCs and help enhance the consistency of RCTM clinical approach and strategy.

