 - i. Status of forms (e.g., consent, completing of screener, baseline assessment battery, etc.)

Data Report.

[name] will also prepare interim analysis reports for review with the DMO. These interim analysis reports will include the following:

1. Recruitment and participant status
 - a. Table 2: Targeted/Planned Enrollment Table
 - b. Table 3: Demographic and key baseline characteristics by group
2. Safety assessment for all participants
 - a. Table 4: Treatment duration for all participants
 - b. Table 5: Adverse events by participant
 - c. Table 6: Serious adverse events by participant
 - d. Table 7: Participant deaths
 - e. Table 8: Participants without capacity to consent during follow-up

Reports from the DMO (largely taken from National Institute of Allergy and Infectious Diseases guidelines).

SOCIAL PROTOCOL (HRP-580)

PROTOCOL TITLE: The Residential Care Transition Module

VERSION DATE: 2/10/2022

At the conclusion of each annual review, the DMO will discuss her/his recommendations and findings with [name]. If necessary, the DMO will also issue a written summary report that identifies key issues in the administrative, safety, and data reports and provides overall safety assessment and recommendations. Any rationale for recommendations will be included where appropriate. The report will not include confidential information. Following dissemination of this report to [name], [name] will provide the report to NIA and the Co-Investigators for review.

The DMO will notify [name] of any findings of a serious nature or recommendations to discontinue all or part of the intervention. [name] will then immediately inform the project officer at NIA of this recommendation.

20.2 Data Safety Monitoring.

A data monitoring safety plan (DMSP) that includes a data safety and monitoring officer is proposed to provide additional oversight of the research protocol and adverse event reporting, if necessary.

The main activities of the DMSP will be as follows (taken from National Institute of Allergy and Infectious Diseases guidelines):

1. Review of interim and cumulative data for any evidence of study-related adverse events (AEs);
2. Review of interim/cumulative data for evidence of efficacy of the intervention;
3. Review of data quality, completeness, and timeliness;
4. Review the adequacy of compliance with goals for recruitment and retention, including those related to the participation of women and minorities;
5. Review adherence to the protocol;

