6. Review factors that might affect the study outcome or compromise the confidentiality of the data (such as protocol violations, unmasking, etc.); and
7. Identification of factors external to the study such as scientific or therapeutic developments that may impact participant safety or the ethics of the study.

Safety reports. In addition to producing administrative reports on an annual basis to the DMO, [name] will generate annual safety reports that will list adverse events, serious events, unexpected events, events related to or associated with the intervention, and the potential causality of the intervention to the event for each participant. If the research team becomes aware of an adverse event or unanticipated problem occurring while a participant is enrolled in the study (from consent through the participant's final data collection), the event will be documented and/or reported per the protocol below. Events will be documented/reported as adverse events per the protocol if they meet one of the following criteria: a participant alerts study staff of a new or worsening health problem that causes the participant to 1) be unable to perform their daily routine, 2) seek medical care (provider visit, hospitalization, residential care placement, etc.), or 3) take a new medication. Conditions existing prior to study enrollment that have not worsened/changed will not be considered adverse events and will not be documented/reported. Per the University of Minnesota IRB guidelines, all events or information that indicates a new or increased risk, or a safety issue, will be promptly reported.

SOCIAL PROTOCOL (HRP-580)

PROTOCOL TITLE: The Residential Care Transition Module

VERSION DATE: 2/10/2022

Taken from earlier National Institutes of Mental Health policy on Data and Safety Monitoring in Clinical Trials, the definition of each event is as follows:

Adverse event. Any untoward medical occurrence in a patient or clinical investigation participant which does not necessarily have to have a causal relationship with the treatment. An adverse event can therefore be any unfavorable and unintended sign (including an abnormal laboratory finding, for example), symptom, or disease temporally associated with the participants' involvement in research, whether or not considered related to participation in the research.

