Serious adverse event. Any adverse experience that results in any of the following outcomes: death, a life threatening experience, inpatient hospitalization, a persistent or significant disability/incapacity, or a congenital anomaly/birth defect. Important medical events that may not result in death, be life threatening, or require hospitalization may be considered a serious adverse experience when based upon appropriate medical judgment, and they may require medical or surgical intervention to prevent one of the outcomes listed in this definition.

Unexpected. Any adverse experience, the specificity or severity of which is not consistent with the risk information described in the [protocol or consent documents].

Related to (or associated with) the intervention. There is a reasonable possibility that the experience may have been caused by the intervention.

Causality. A reasonable possibility that the product is etiologically related to the adverse event. Causality assessment includes, for example, assessment of temporal relationships, dechallenge/rechallenge information, association with (or lack of association with) underlying disease, presence (or absence) of a more likely cause, plausibility, etc.

Survey responses regarding health information will not be considered adverse events, unless otherwise communicated to the study staff. [Note: Medical events or emergencies of a non-participant will not be considered/document as adverse events]. Regardless of the classification of an event (adverse event versus serious adverse event), only those events determined to be potentially related to the participant's involvement in research will be reported to IRB promptly. All other adverse events reported to study staff by participants will be recorded and reported annually via routine reports. Any participant deaths will also be promptly reported, regardless of the cause.

In the instance of an adverse event, [name] and/or the study team will classify whether the event is unexpected, adverse, or seriously adverse, whether the event is unexpected or related to the intervention, and what potentially caused the event. Per the protocol, [name] will review the data routinely and will alert both the DMO as well as NIA as needed if these events occur.

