All AEs (following consent) will be collected on an adverse event form, in electronic format. AEs experienced by a participant during a study procedure (i.e. intervention/survey) and are considered potentially related to the participant's involvement in research will be reported within 5 days of discovery to the University of Minnesota IRB (per the University's IRB procedures) and annually to the NIA, DMO, and IRB in data monitoring reports.

AEs that occur outside of the context of a study procedure (i.e. intervention/survey), as well as those that are determined to be not related to the participant's involvement in the study, will be

SOCIAL PROTOCOL (HRP-580)

PROTOCOL TITLE: The Residential Care Transition Module

VERSION DATE: 2/10/2022

documented via the team's electronic AE form and included in the annual report (to be shared with IRB, DMO, and NIA Program Officer).

SAEs that are unanticipated and related to the intervention will be reported to the IRB, NIA Program Officer, and to the DMO within 48 hours of our team's knowledge of SAE. The summary of all other SAEs (i.e. those determined not related to study involvement) will be included in the annual report (to be shared with IRB, DMO, and NIA Program Officer).

Deaths determined not-related to the study will be reported to the IRB within 5 days of the team's knowledge of the participant's death, and reported to the Safety Officer and NIA Program Officer via routine annual reports. Though unlikely, if a participant's death during the project enrollment has a possible relationship to the study, it will be reported in expedited fashion (within 24 hours of the team's knowledge of a participant's death) to the University of Minnesota IRB, the NIA Program Officer, and to the DMO. A written SAE report will be submitted soon thereafter.

No adverse events are expected to be related to study involvement. However, due to the nature of our study population, possible adverse events (i.e. general medical events and/or emergencies) may occur during the time a participant is enrolled in the study. These events will be documented and/or reported according to the protocol.

[name] will present the safety report to the DMO to ensure that there are no negative effects of the treatment. The DMO will review the safety reports annually to ensure that the proper procedure was followed and to identify any potential trends in the data. [name] will present the safety reports to NIA if adverse events occur.

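### Adverse events are captured only when participants alert staff, and staff contact differs by arm, so by-arm adverse event counts would rest on unequal ascertainment

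*Combined protocol and SAP*

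**What the plan says.** **Capture.** Under Safety reports in section 20.2, an event is documented when "a participant alerts study staff of a new or worsening health problem that causes the participant to" lose their daily routine, seek medical care or start a new medication. The same section states: "Survey responses regarding health information will not be considered adverse events, unless otherwise communicated to the study staff". Events not judged potentially related to the research follow the annual route: "All other adverse events reported to study staff by participants will be recorded and reported annually via routine reports". No scheduled adverse event question is described.

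**Contact.** Section 4.1 gives the RCTM arm six sessions in 4 months, the first three weekly and the last three monthly: "The duration of each session is about 45 to 150 minutes each". It also offers ad hoc counseling by telephone or email. Section 5.3 adds "Quarterly follow-up calls by the TC to all participants", with an open question about how the caregiver is doing. Section 5.2 (Usual Care) puts a call at about 15 minutes and lets controls contact the counselor themselves.

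**Review.** Section 20.2 sends the safety report to the DMO "to ensure that there are no negative effects of the treatment", and the DMO also looks for trends. In the Data Report list of section 20.1, the adverse event table is titled "Table 5: Adverse events by participant". The serious event table has the same layout, and the deaths table names no grouping. Only the baseline table (Table 3) is specified by group.

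**The concern.** A capture rule that waits for the participant to speak depends on how often there is someone to speak to. Here that differs by randomized arm, and the source that does not differ, the blinded 4-, 8- and 12-month surveys of section 5.3, is excluded by rule.

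Section 20.2 expects general medical events in this population. Telling whether the intervention adds to them calls for the control arm as a reference. If the DMO looks at counts or trends by arm, two errors are possible. More contact may yield more recorded events in the RCTM arm with no harm behind them. Or a real excess may be hard to separate from the extra contact. This matters because section 20.1 allows the DMO to recommend discontinuing all or part of the intervention.

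**Working it through.** The documents give no figure for adverse event ascertainment, so there is none to reproduce. The check counts scheduled contacts and then asks what those counts could do to recorded events when true rates are equal.

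**1. Scheduled counselor contact over 12 months.** Inputs: six sessions of 45 to 150 minutes (section 4.1) and quarterly calls of about 15 minutes (sections 5.2 and 5.3). Assumed: four calls per arm, the same call length in both arms, and no ad hoc contact.

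- Contacts: RCTM 6 + 4 = 10; control 4. Ratio 10/4 = 2.5.
- Minutes: RCTM 6 × 45 + 4 × 15 = 330 up to 6 × 150 + 4 × 15 = 960; control 4 × 15 = 60. Ratio 5.5 to 16.
- Months 0 to 4: 6 + 1 = 7 contacts versus 1. After month 4: 3 versus 3.

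**2. Small, constant chance of mention per contact.** Assumed: sessions at months 0.25, 0.5, 0.75, 1.75, 2.75 and 3.75; calls at months 3, 6, 9 and 12; events spread evenly over time. A contact at month t can pick up events from the preceding min(t, L) months, where L is the recall window. The expected recorded ratio is the sum of min(t, L) over all RCTM contacts divided by the same sum over control contacts.

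| Recall window | Sessions | Calls | Ratio, 12 months |
|---|---|---|---|
| Unlimited | 9.75 | 30 | 39.75/30 = 1.33 |
| 3 months | 9.0 | 12 | 21/12 = 1.75 |
| 1 month | 4.5 | 4 | 8.5/4 = 2.1 |
| 1 week (0.25 month) | 1.5 | 1 | 2.5/1 = 2.5 |

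The contact ratio of 2.5 is thus reached only if events go unmentioned after about a week.

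**3. Larger chance of mention per contact.** Let q be the chance that one contact reveals an event, and k the number of contacts within the recall window after it. The event is recorded with probability 1 − (1 − q)^k, averaged over event times. With q from 0.2 to 0.8 and nearly the same timings (monthly sessions at months 1.7, 2.7 and 3.7), the RCTM-to-control ratio is:

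| Recall window | Events in months 0–12 | Events in months 0–4 |
|---|---|---|
| Unlimited | 1.00–1.13 | 1.00–1.28 |
| 3 months | 1.07–1.49 | 1.22–2.46 |
| 1 month | 1.75–2.01 | 3.99–5.00 |

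**4. What this could look like in counts.** Purely for illustration, assume a true risk of 40% in both arms of 120. With 80% of events recorded under RCTM and 60% under control, expected counts are 120 × 0.4 × 0.8 = 38 and 120 × 0.4 × 0.6 = 29. A two-sided 0.05 test would then be significant about 28% of the time. With 80% and 40% recorded, the counts are 38 and 19, and the figure is 83%. The plan specifies no such test; the numbers only show how far a by-arm reading could mislead.

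**The case against.** The strongest reply is that the safety report is a case review. Section 20.2 has it list events and judge the intervention's possible role for each participant, from timing, underlying disease and plausibility. Section 17 plans no between-arm analysis of adverse events. Unequal counts do not invalidate that review. This stands, and a reader who inferred that the safety check cannot be carried out would go beyond the documents. It does not cover the trends that the DMO is also asked to find. Case judgments are also made by the investigator or study team, with no masking to arm stated.

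Second, the main foreseeable risk to caregivers in section 14.1, apart from confidentiality, is psychological. Stress and depressive symptoms are surveyed in both arms by blinded staff, so worsening would show in the outcome data. This also stands, although those outcomes are not among the listed safety tables.

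Third, counselor contacts are not the only staff contacts. Disposition contacts, reminders and surveys, some by telephone, reach both arms. Adding three survey contacts per arm gives 13/7 = 1.9 instead of 2.5. Controls may also call in. This narrows the gap in contact without closing it. Ad hoc counseling, not counted, would widen it.

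Fourth, a reader might infer that listing events by participant causes bias or hides the arm. It does neither. Section 20.1 gives table titles only, and nothing says that arm is withheld; the titles simply specify no comparison.

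Fifth, over-recording under RCTM errs toward caution. That is the expected direction, and the documents do not support a reading that harm is being concealed. A false signal still has a cost, and an excess that might be due to contact is hard to act on.

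**Conclusion.** The concern holds as a structural risk, not as a measured bias. A stated rule leaves out the source that is scheduled alike in both arms, and the remaining source depends on contact that differs by arm in the first 4 months. By-arm counts or trends may therefore show a spurious RCTM excess or leave a real one hard to interpret.

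With no true difference, the recorded ratio over 12 months runs from about 1.0 to about 2 under the assumed recall windows, and for months 0 to 4 from about 1.0 to about 5. It would be tempting to take 2.5 as the expected 12-month distortion, but it is a ceiling for scheduled contact. These figures rest on assumed call numbers, contact timings, recall windows and chances of mention, none of which the documents give beyond the session schedule.

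Deaths are less exposed, because all are reported whatever the cause, though staff must still learn of them. This is a cheap improvement to the monitoring reports and does not affect the primary analysis.

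**What to change.** 1. Present Tables 5 to 7 of the Data Report by arm, keeping the participant listings.
2. Tag each event by source: session, ad hoc contact, quarterly call, participant-initiated contact, or contact around a survey.
3. Show contact counts by arm beside the event counts. The counselor already logs the frequency and duration of RCTM sessions (section 5.3, Treatment fidelity) and of control calls (section 5.2, Usual Care).
4. As a supporting comparison, tabulate by arm whatever health items about the caregiver the 4-, 8- and 12-month surveys already collect. Section 5.2 describes the baseline survey as covering physical health, but the health events it names are those of the person with ADRD, whose events section 20.2 does not count. The documents do not show that follow-up items match the adverse event criteria, so this table supplements the event tables and does not replace them. Footnote the modified bereavement survey and the drift in survey timing after late returns (section 5.3).
5. Leave expedited reporting unchanged, and keep the by-arm tables from the blinded survey assistants.

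The cost is a few extra tables a year, a source field on the event form, and more minor events shown to the DMO. No new participant data collection is needed, because step 4 uses only items already in the surveys.

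### The study team's own relatedness call decides whether the DMO hears of a serious event within 24–48 hours or only in the annual report, and a non-fatal SAE called not related has no fixed prompt route to the DMO, NIA or IRB

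*Combined protocol and SAP*

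**What the plan says.** Section 20.2 (Data Safety Monitoring, safety reports) gives classification to the study side: a role whose name is removed "and/or the study team will classify whether the event is unexpected, adverse, or seriously adverse". The same parties also judge relatedness and possible cause. No section asks the DMO, or anyone else outside the team, to confirm that call when the event occurs.

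The reporting route then follows from the call:

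- An SAE that is unanticipated and related goes to the IRB, the NIA Program Officer "and to the DMO within 48 hours of our team's knowledge of SAE".
- For a death with a possible link to the study, "it will be reported in expedited fashion (within 24 hours of the team's knowledge of a participant's death") to the IRB, the NIA Program Officer and the DMO.
- For SAEs called not related: "The summary of all other SAEs (i.e. those determined not related to study involvement) will be included in the annual report", which goes to the IRB, DMO and NIA.
- For deaths called not related: "Deaths determined not-related to the study will be reported to the IRB within 5 days" of the team learning of them, "and reported to the Safety Officer and NIA Program Officer via routine annual reports".

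The DMO reviews the safety reports once a year. The section also states in advance: "No adverse events are expected to be related to study involvement".

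**The concern.** The call that opens the fast route is made by the people running the trial. If they wrongly call an event not related, the same call delays the review that could question it.

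This matters most where relatedness is hard to judge. Section 14.1 rules out physical risk and names psychological risk as the possible harm to caregivers. A psychiatric admission during the counseling period would count as an SAE, because inpatient hospitalization is in the section 20.2 definition, and its link to the intervention could be open to argument. Section 14.1 relies partly on excluding caregivers with serious psychiatric illness, but sections 9.1 and 9.2 list no such exclusion and admit caregivers on stable psychotropic medication. Such events therefore cannot be assumed away.

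At stake is whether the DMO, who under section 20.1 may recommend stopping all or part of the intervention, learns of such an event while the participant is still in counseling.

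**Working it through.** The plan gives no figure to reproduce. The check sets the section 20.2 routes side by side and then does simple arithmetic on the intervals.

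| Event and team's call | IRB | DMO | NIA |
|---|---|---|---|
| Death, possibly related | 24 hours | 24 hours | 24 hours |
| SAE, unanticipated and related | 48 hours | 48 hours | 48 hours |
| Death, not related | 5 days | annual (to the Safety Officer) | annual |
| Non-fatal SAE, not related | annual | annual, as a summary | annual |

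The last row is the only one in which no recipient has a fixed prompt deadline.

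Next, does any other text supply one?

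1. Section 20.2 says the data are reviewed routinely and the DMO and NIA alerted as needed. It gives no trigger and no deadline, and the study side decides.
2. Section 20.2 promises prompt reporting of every participant death. It names no recipient there, covers deaths only, and the later text sends deaths called not related to the Safety Officer annually.
3. Section 20.2 promises prompt reporting of anything showing a new or increased risk, under IRB guidelines. It sets no DMO deadline, and the study side must first recognize the risk.
4. Section 20.2 limits prompt IRB reporting of events, other than deaths, to those judged potentially related. This closes the IRB route for the last row.
5. Section 20.1 says the DMO is notified of adverse events, but defers to the same specifications.

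The wait for the DMO:

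- Inputs: one report a year (12 months, section 20.2); intervention length 4 months (sections 1.1 and 4.1).
- Fast route: 24 hours = 1 day; 48 hours = 2 days.
- Longest wait after a not-related call: 12 months, and 12 / 4 = 3 times the intervention.
- Assumption: events fall evenly over the reporting year. Average wait = 12 / 2 = 6 months. Share waiting longer than 4 months = (12 − 4) / 12 = 8/12, about two thirds.

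An event during counseling that waits more than 4 months would usually reach the DMO after that participant's sessions have ended.

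One adjacent gap: the 48-hour rule needs an SAE to be both unanticipated and related, while the remaining SAEs are glossed as those not related. A related but anticipated SAE therefore has no clear expedited route to the DMO.

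**The case against.** The strongest reply is that a reader might infer that deaths and serious events are never checked outside the team, and the documents do not support that. The IRB learns of every death within 5 days whatever the call, so a suicide would reach an outside body promptly. The as-needed alert and the new-risk provision mean the DMO may well hear of events between annual reviews. The Co-Investigators also review adverse events (section 23.0), so the DMO is not the only reviewer. The threshold for the fast route is low: a reasonable possibility for relatedness, and a possible relationship for a death. The IRB judged the study to be no more than minimal risk (section 22.6), and team classification with annual DMO review is a stated choice.

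All of this stands, and it narrows the point. For deaths, the gap is only that the DMO and NIA are not told when the IRB is. For non-fatal SAEs called not related, the reply does not close the gap. The IRB is not told promptly, the Co-Investigators belong to the study side, the alert is discretionary, and a low threshold still has to be applied by the team.

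Timing also counts. On the planned schedule (start June 2016, RCTM delivery through month 55), counseling would have ended around December 2020, before this version of February 2022. If that schedule held, the change cannot help anyone during counseling. It would serve participants still enrolled, because adverse events are recorded until final data collection, and it would improve the plan if reused.

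**Conclusion.** The point holds in limited form. The team's own call fixes whether the DMO hears within 1–2 days or in the annual report, and a wrong not-related call on a non-fatal SAE may go unchecked outside the study side for up to 12 months. This is a minor weakness in oversight, worth fixing because the fix is cheap. It does not show that any event was or will be misclassified.

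The conclusion assumes that Safety Officer means the DMO. That is reasonable, since section 20.2 mentions a data safety and monitoring officer, but the term is not defined. The 6-month average and the two-thirds share also assume an even spread of events; the 12-month maximum needs only the annual cycle.

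Three further readings go beyond the text. A reader might infer that the counselors judge relatedness; section 20.2 says only the study team, and nothing assigns the task to them. A reader might take the DMO to be independent; section 20.1 describes a senior faculty member at the same university and does not use that term. And a reader might size the problem by the number of caregivers enrolled between reviews; the documents give no rate of SAEs or of wrong calls, so enrolment does not measure it.

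**What to change.** Three wording changes in section 20.2:

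1. Copy the DMO and the NIA Program Officer on the death notice already sent to the IRB within 5 days, whatever the relatedness call.
2. Forward the electronic adverse event form for each SAE to the DMO when it is completed, whatever the call, so that the DMO can query it. This also covers the related but anticipated SAE.
3. State that Safety Officer means the DMO.

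The notice, the form and the DMO role are already in the plan. The cost is a few extra messages and some DMO reading of events that prove unrelated. No treatment, endpoint or analysis changes. A mandatory second adjudication of every SAE, with the event treated as related if either party says so, would be a new duty. Its value is debatable in a minimal-risk study, and it is not needed to close this gap.
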